7.0 TREATMENT PLAN

7.1 Treatment Plan Overview

SCHEMA

7.2 Administration of IP or Placebo

Home-based Exercise Intervention Arm: Participants will meet with the exercise physiologist at the Prevention Center for a 60 minute one-on-one session. Participants who are not willing or able to go to the Prevention Center for an in-person session may have this session conducted through Telehealth (HIPAA-compliant videoconferencing). They will receive an individualized exercise prescription with an ultimate goal of moderate aerobic exercise for 150 minutes per week. Exercise prescriptions will be modified as appropriate for those with neuropathy, lower extremity edema, or other physical limitations or medical conditions (76, 77). Various exercises such as brisk walking, aerobics, and cycling will be suggested, with instruction on proper exercise techniques and safety (such as warm-up or stretching). Slow implementation of the exercise goals will reduce chances of injury and increase participant adherence and sense of accomplishment. The session length and exercise intensity will gradually increase over the first eight weeks to the ultimate goal and will be maintained for the rest of the study period. Participants will learn to determine exercise intensity levels using the Borg rating of perceived exertion scale, a validated tool for monitoring and prescribing exercise intensity that correlates well with heart rate (78). After each exercise session, participants will log their duration, perceived intensity, and exercise activity. They may complete their exercise log on paper or electronically. Participants opting to complete the daily exercise logs on paper rather than electronically will be asked to mail their exercise logs in weekly in a study-provided stamped addressed envelope. If they prefer, they may also photograph the week's exercise log and email or text it to the study coordinator.

A sample progression of exercise goals is provided below, but the specific exercise prescription will be individualized by the exercise physiologist based on participant's initial level of fitness and physical functioning, as well as progress made throughout the study.

Week #	Total # of Exercise Sessions Per Week	Minutes of Aerobic Exercise Per Session	Total Minutes Per Week	Rate of Perceived Exertion (RPE, Borg 6-20 scale)
1	3	15	45	9-11
2	3	20	60	9-11
3	3	25	75	9-11
4	3	30	90	10-12
5	4	30	120	10-12
6	4	30	120	11-13
7	4	30	120	11-13
8-24	5	30	150	12-14

Behavioral support: The exercise physiologist will contact participants weekly by phone. The purpose of the phone calls will be to provide motivational support, troubleshoot barriers to exercise, and to adjust training intensity and progression throughout the intervention. The exercise physiologist will ask participants whether they experienced any excessive fatigue, muscle soreness, injury, or other symptoms during the past week. During each phone call, the exercise physiologist will provide assistance with overcoming barriers to exercise, provide an update exercise prescription for the upcoming week, and encourage flexibility/stretching exercises. Although weekly phone calls are preferred, the exercise physiologist may reach out to the participant via email (if the participant agrees) to discuss progress over the past week if the exercise physiologist and participant are unable to schedule a mutually agreeable time for a phone conversation. Participants will also have the opportunity to contact the physiologist via email if they desire.

Participants will receive written materials on exercise techniques and motivational strategies, as well as general information about ovarian cancer and survivorship. Participants will be logging their exercise daily, and they may view/track their weekly progress (self-monitoring). If participants have not completed their exercise log for more than a week, they will be reminded to complete them by the exercise physiologist during their weekly telephone call or will receive a reminder by the study coordinator. "Badges" will be awarded electronically for accomplishments such as meeting 75% or 100% of a weekly exercise goal. Badges will be built into REDCap and appear at the end of the week once a participant has entered their exercise log data. Participants may opt out of any portion of this e-technology at any time. Participants who choose to fill out the exercise logs on paper rather than electronically will be asked to mail each week's completed exercise log back in a self-addressed stamped envelope provided by the study coordinator after she has spoken with the exercise physiologist during her weekly telephone call. If participants prefer, they may also photograph the week's exercise log and email or text it to the study coordinator.

Wait-list Control Arm: Participants will continue their usual activities. They will be offered the same home-based exercise intervention (with behavioral support), after completing their 24 week assessments. At the start of the study, participants in the control arm will receive general education materials about ovarian cancer and survivorship. After 24 weeks, they will be given the written materials on exercise techniques and motivational strategies, and offered the exercise intervention.

7.3 Concomitant Medication and Supportive Care Guidelines

All participants on either arm of the study may receive any care deemed beneficial by themselves or their treating physicians. They may take any medications or treatments indicated for concomitant medical conditions. Participants experiencing muscle soreness or discomfort as a result of exercising may take supportive over-the-counter medications including acetaminophen, non-steroidal anti-inflammatory drugs, and other analgesics (as long as they have not been instructed by their doctor to avoid those medications due to medical contraindications) or any medications prescribed by their physician. They may also apply ice or heat for symptomatic relief. In the event of a suspected injury, participants will be instructed to seek medical evaluation and treatment as indicated.

7.4 Duration of Therapy

After baseline assessments (done at FHCRC Prevention clinic or home-based, see section 8.1) and randomization, participants randomized to the exercise arm will receive a one-on-one session with the exercise physiologist for one hour either at the FHCRC Prevention Center or through Telehealth. The exercise intervention will last for 24 weeks. During the intervention, they will not have any clinic visits. They will receive weekly telephone calls for support. All assessments during the intervention (actigraphy, surveys) will be completed at home. At the end of the study, all participants (exercise intervention arm and wait-list control arm) will complete end-of-study assessments either at clinic, or home-based (see section 8.1). After 24 weeks, participants in the wait-list control arm will be offered the home-based exercise intervention, which would also last for 24 weeks. Participants receiving the delayed intervention will be offered the single one-on-one session with the exercise physiologist and receive weekly telephone calls for support, but will not have any additional clinic visits or any assessments during or after the delayed intervention. Participants who were enrolled but ultimately became ineligible by falling significantly outside of the eligibility window (within 6 months of completing chemotherapy) before the baseline visit could occur due to COVID-19 related delays in visit scheduling. They may receive the exercise program without any data collection activities if they have a strong interest. We anticipate this to be a rare event going forward since baseline visits will now be allowed remotely, but rarely occurred previously due to prior COVID-19 related delays in Prevention Center scheduling and patient concern about visit timing.

7.5 Duration of Follow-Up

Refer to section 8.0 for the evaluations to be done at baseline, during the 24 week intervention, and at the 24 week time point. After the end-of-study visit, there will be no further study assessments or follow-up. Participants who are randomized to the control arm will be offered the delayed exercise intervention after 24 weeks (which will include a one-on-one session with the exercise physiologist and weekly telephone support), but this intervention is optional, and in addition, there will not be any other assessments or clinic visits.

7.6 Dosing Delays/Dose Modifications

If a participant has a suspected injury as a result of exercise, she will be assessed by a physician. Subsequent exercise will either be held to allow for recovery, or modified, depending on the nature of the injury and physician assessment. If a medical issue develops which is not related to exercise, the exercise prescription will also be modified if needed.

Participants who are receiving maintenance chemotherapy may exercise, but have a few special considerations:

- If a participant develops anemia, she will notify the exercise physiologist and the exercise prescription may be modified. She may need to decrease the intensity or amount of exercise.
- Individuals with a hemoglobin of less than 8 will be instructed to hold exercise until their anemia is improved above this threshold.
- Individuals with neutropenia (low white blood cell count) may have a reduced ability to fight infection and will take precautions (for example, use caution in public exercise facilities, ensure proper cleaning and sterilization of equipment).
- Individuals with a fever (temperature >100.4 degrees Fahrenheit) will avoid exercise until they have not had any further fevers for 24 hours.

Protocol 10045

- Individuals with low platelet count may have increased risk of bleeding or bruising; they will avoid contact sports or activities with a high risk of falling if platelets are less than 100,000, but may continue other physical activities. They will abstain from exercise if their platelet count is <50,000. Exercise may be resumed when platelets return to above this threshold.

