2.0 INTRODUCTION TO THE PROTOCOL

2.1 Introduction

The majority of people with ovarian cancer present with advanced-stage disease (1). Although individuals usually achieve initial remission, most experience recurrence and die of chemoresistant disease, with a five-year survival rate of 27% (1). Ovarian cancer and its treatments are associated with a variety of persistent negative side effects including depression, anxiety, fatigue, and reduced quality of life (2-5). Physical activity may help cancer survivors reduce distress, improve quality of life, and possibly improve survival.

Two observational studies suggest that physical activity is associated with better quality of life in ovarian cancer survivors (6, 7), which is important because ovarian cancer survivors have persistently reduced quality of life even after treatment is completed (2-4). However, only 31% of ovarian cancer survivors achieve public health guidelines for physical activity (7). A Cochrane review of randomized controlled trials in cancer survivors (multiple cancer types) found that short-term exercise improved physical functioning, cancer-related fatigue, and quality of life (8). The effectiveness of exercise training is especially well studied in breast cancer survivors (9, 10). Whereas most people with breast cancer are diagnosed with early-stage disease, the majority of individuals with ovarian cancer are diagnosed at advanced-stage, undergo intensive chemotherapy, and have worse quality of life. The efficacy of exercise is understudied in ovarian cancer, and our study is significant because identifying interventions that can benefit ovarian cancer patients is an unmet need.

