9.0 SUBJECT DISCONTINUATION FROM STUDY

Subjects may be removed from this study at any time at their discretion. Subjects may also be removed from this protocol if they develop any untoward side effects from the study intervention.

Cancer recurrence does not mandate study discontinuation. If a subject develops cancer recurrence, they may still continue on the study if they are willing and able. Exercise is safe for individuals with cancer who are undergoing active treatments including chemotherapy. The exercise physiologist may alter their exercise prescription as needed based on the individual's functional ability and medical condition. If a participant desires to discontinue the study, she may discontinue the study at any time. If an individual desires to stop exercising but is willing to complete study assessments, she will complete originally planned study assessments (including clinic visit) at the originally specified time points.

An explanation for discontinuing the study is recorded for each subject discontinuing the study on the appropriate CRF/eCRF. Treatment in this study must be discontinued for any of the following reasons:

- if the PI decides to stop the study;
- at Investigator's discretion;
- at the subject's request;
- Grade 4 or life-threatening toxicity (See Section 11, Adverse Events) attributable to study intervention

Target enrollment is 98 participants, accounting for up to 20% drop-out. Power calculations are based on 78 participants. Additional subjects may be enrolled in the study to replace individuals who have dropped out in order to achieve the goal of 78 participants completing the study.

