13.7 Exploratory Analysis

In exploratory subgroup analyses, we will apply the GEE models for the primary analysis given above to study the intervention effect on each of the primary outcomes among participants who developed (versus those who did not develop) recurrence over the course of the study. The GEE models will also be applied to additional exploratory subgroup analyses to assess the intervention effects on the primary outcomes by chemotherapy maintenance group (if the sample size is sufficient).

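### The blood-count and fever rules in 7.6 are written only for maintenance chemotherapy, so participants exercising during chemotherapy for recurrence have no fixed holds

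*Combined protocol and SAP*

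**What the plan says.** Section 7.6 opens with a paragraph for all participants: a suspected exercise injury is assessed by a physician, and the prescription is changed if needed for an unrelated medical problem. A separate list follows, introduced by "Participants who are receiving maintenance chemotherapy may exercise, but have a few special considerations". The list contains:

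- anemia: tell the physiologist, and hold exercise at a hemoglobin below 8;
- neutropenia: precautions, with no numeric cut-off;
- fever above 100.4 F: no exercise until 24 hours have passed without fever;
- platelets: avoid contact sports and activities with a high risk of falling below 100,000, and then "They will abstain from exercise if their platelet count is <50,000".

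Section 9.0 deals with recurrence: "If a subject develops cancer recurrence, they may still continue on the study if they are willing and able". It adds "Exercise is safe for individuals with cancer who are undergoing active treatments including chemotherapy" and then "The exercise physiologist may alter their exercise prescription as needed", according to function and medical condition. It does not refer to 7.6. Its one mandatory stop based on toxicity is "Grade 4 or life-threatening toxicity (See Section 11, Adverse Events) attributable to study intervention".

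The protocol foresees recurrence. Section 2.1 says of people with ovarian cancer that "most experience recurrence and die of chemoresistant disease", and section 13.7 plans a subgroup analysis of "participants who developed (versus those who did not develop) recurrence over the course of the study".

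**The concern.** At the same known blood count, the text treats two participants differently and gives no reason. With platelets of 40,000, a participant on maintenance chemotherapy must stop exercising. A participant on chemotherapy for recurrence is left to the physiologist's judgment. The fever instruction has no stated reason to depend on treatment at all.

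Delivery is remote. Section 7.4 has no clinic visits during the 24-week intervention and no assessments during the delayed one. Section 9.0 names the exercise physiologist as the person who may change the prescription. A written threshold is useful in that setting. What is at stake is participant safety; the efficacy analysis is not involved.

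**Working it through.** No sample size, power or alpha figure is involved. The check compares the scope of the provisions and then works out when the gap could arise.

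**1. Does the lead-in reach treatment for recurrence?** Section 5.1.3 allows maintenance therapy only while the participant is in clinical remission. Chemotherapy given because the cancer has returned is therefore not maintenance in the protocol's own usage. Section 9.0, which does cover that participant, does not import the 7.6 list.

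**2. Does anything else supply the thresholds?** The four are hemoglobin <8, platelets <50,000, platelets <100,000 and temperature >100.4 F.

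| Provision covering everyone who exercises | Content | Thresholds present |
|---|---|---|
| 4.2 | Symptom-based stop list; prescription changed as needed for unrelated medical problems | 0 of 4 |
| 7.2, individual prescription | Adapted as appropriate for physical limits or medical conditions | 0 of 4 |
| 7.2, weekly call | Asks about fatigue, soreness, injury and other symptoms; updates the prescription | 0 of 4 |
| 7.6, first paragraph | Physician assessment of injury; change if needed | 0 of 4 |
| 9.0 | Physiologist may alter the prescription; investigator discretion | 0 of 4 |

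The mandatory toxicity stop in 9.0 requires attribution to the study intervention, so a low count caused by chemotherapy does not trigger it. Section 4.1 sets no stopping rules.

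**3. When could recurrence treatment overlap with exercise?** Inputs: screening 1 to 6 months after chemotherapy (5.1.3); exercise in weeks 0–24 for the exercise arm, 49 planned (13.4); exercise in weeks 24–48 for wait-list participants who opt in, up to 49 (7.4, 13.4).

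Weeks per month = 365.25 / 12 / 7 = 4.348.

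- Exercise arm: 24 / 4.348 = 5.5 months, so exercise ends 1 + 5.5 = 6.5 to 6 + 5.5 = 11.5 months after chemotherapy.
- Wait-list opt-in: 48 / 4.348 = 11.0 months, so exercise ends 12.0 to 17.0 months after chemotherapy.

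Any delay between screening and baseline pushes these later. The documents give no recurrence rate within these windows, so the calculation locates the exposure without counting participants.

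**4. What about the maintenance drugs themselves?** Section 5.1.3 names hormonal agents, anti-angiogenesis agents, PARP inhibitors and immunotherapy. Read literally, 'maintenance chemotherapy' covers none of these classes. This part is less certain, because the drafters may have meant all maintenance therapy; 13.7 uses similarly loose wording.

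**The case against.** The strongest case on the other side is that the list was never meant to be narrow. A literal reading leaves it almost without a population, and several bullets are phrased for any participant or individual. Staff might well apply them to everyone. A physiologist told of a low count already has the authority to hold exercise and, through the weekly call and updated prescription, the occasion to do so. Section 7.2 also requires prescriptions to be adapted for medical conditions. Treating oncologists remain in charge of care (7.3), and Appendix C schedules no safety blood counts, so a rule can act only after someone else has found the count. The symptom list in 4.2 would catch some anemia. The consent form, which was not available for this review, may state the instructions more broadly.

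Much of this stands as a limit on weight. The gap is smaller in practice than on paper, and the point about the named maintenance classes is uncertain. The objection does not close the gap for recurrence. Even a loose reading of the lead-in does not clearly cover treatment after remission has ended, and every general provision is conditional or discretionary and has no count or temperature threshold. Oncology care is equally present for maintenance patients, yet the protocol still gives them fixed holds. If broad use was intended, the amendment simply says so.

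**Conclusion.** The concern holds. All four numeric thresholds and the neutropenia precaution are confined by their lead-in to maintenance chemotherapy. A participant exercising during chemotherapy for recurrence, a situation the protocol expressly allows, has only general and discretionary cover.

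Confidence is high for recurrence treatment and lower for the maintenance classes in 5.1.3. The conclusion assumes that the lead-in governs its list and that no text outside the material reviewed extends it. Up to 98 planned participants (49 + 49) could exercise under the protocol, but that is only a ceiling on exposure. The number who would exercise on recurrence treatment with a known low count or fever cannot be derived from the documents. This should be corrected because it is an inexpensive safety improvement.

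**What to change.** 1. In the 7.6 lead-in, replace 'maintenance chemotherapy' with *maintenance therapy or any other systemic anticancer therapy, including treatment for recurrence*. This also settles the uncertainty over the 5.1.3 classes.
2. Move the fever instruction out of the list so that it applies to all participants.
3. In section 9.0, after the sentence on altering the prescription, add *and the considerations in 7.6 apply*.

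Keep every threshold as it is. Widening the whole list to all participants would also close the gap and may be simpler to word.

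The cost is a short amendment and occasional extra exercise holds. It adds no blood-count monitoring, because the rules act only once a count or fever is known. Sample size, power and type I error are untouched.

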7.7 End of Treatment (EOT) Visit Schedule and Procedures

Subjects who discontinue from the study will not require a clinic visit. They may continue their usual clinical care with their treating physicians. The reason for study discontinuation will be recorded. Participants who desire to stop exercising will be asked whether or not they are willing to complete study assessments. If they are willing, they will complete originally planned study assessments (including clinic visit) at the originally specified time points.

7.8 Emergency Unblinding Procedures

- *Not applicable*

8.0 SUBJECT EVALUATION

8.1 On-Study Clinical Evaluations

Clinical evaluations take place according to the Study Calendar (Appendix C). Baseline assessments will occur prior to randomization, and whenever possible no later than 1 month after informed consent is signed. End-of-study assessments will occur at 24 weeks. The window between this end-of-study visit should be as close to 24 weeks as possible. The study team will make every effort to schedule this visit between 22 weeks and 26 weeks. Baseline and end-of-study visits originally were conducted at the FHCRC Prevention Center. Due to the COVID-19 pandemic and desire to expand clinical trial access to those who are unable or unwilling to travel to Seattle, participants will now be given a choice to have study assessments performed in clinic at the Prevention Center, or near to home/ at home. Participants desiring to avoid clinic visit will have blood collection performed at a local laboratory and continue to collect saliva at home. Collected blood and saliva will be shipped overnight to the FHCRC Prevention Center for specimen processing and storage. Urine collection, vitals, and anthropometrics will be omitted.

Additional assessments (such as surveys or actigraphy) will be performed at intervals throughout the study, but these assessments will be done at home. These assessments will be scheduled according to the Study Calendar, at the specified time point \pm 2 weeks, or as close as possible to that time window.

The following tests and procedures are completed, although not all tests may be done at each assessment point; see the detailed study timeline in Appendix C.

- **Anthropometrics and vitals:** Blood pressure, resting pulse, weight (in light clothing but without shoes), height (without shoes), waist (smallest diameter) and hip (largest diameter) circumferences. BMI (kg/m^2) will be calculated as weight (kg) divided by height squared (m^2). Participants who opt against a clinic visit will weigh themselves at home and report to us. If available, a recorded height will be abstracted from medical records, and if not available, self-report from the participant will be used. Vitals and anthropometrics will be omitted.
- **Medication Assessment:** Detailed information on use of medications (prescription and non-prescription, including supplements and vitamins) will be collected by a medical assistant at each clinic visit, including drug name, dose, and frequency of use. Participants will be asked to provide a detailed list of their medications to the best of their ability and they will also bring in all of their medications in their original bottles with labels. Study staff will review this information and interview the participant to obtain an accurate, complete medication list. Participants who opt against a clinic visit will be asked to provide a list of prescription and non-prescription medications including drug name, dose, and frequency of use. Study staff can also abstract information based on photographs of medication labels provided by participants and interview as needed. **Daily Physical Activity Log:** Exercise diaries measure daily exercise reliably and have been validated by comparison with physiological measures of compliance such as VO_2 max (79). Intervention arm participants will complete a daily Physical Activity Log at home throughout the study. They will record type of exercise activity, duration, intensity, location (outdoors/indoors), and whether it was performed alone or with others. Participants will complete the Physical Activity Logs either online or on paper; participants completing the Physical Activity Logs on paper will mail them to the study coordinator each week (in stamped addressed envelopes provided by the study).
- **Actigraphy:** Participants will wear a monitor continuously for one week (except during showers/bathing and swimming) at the specified time points. Since self-report may lead to overestimation of exercise adherence, the use of actigraphy to objectively measure exercise intensity and amount adds significant strength to our study (80). Actigraphy will also allow a preliminary evaluation of a dose-response relationship between exercise and our outcomes of interest, and will measure sleeping habits, of interest since sleep disturbances are prevalent in cancer survivors (81). The actigraph will be worn around the waist. Participants will be mailed the actigraph prior to the assessment point, along with instructions, and will mail it back to the study coordinator after the week of use. The actigraph data will be downloaded and the actigraphs will be cleaned using alcohol swabs prior to being mailed back for next use.

Questionnaires (Appendix D) – all questionnaires will be completed at baseline, 12, and 24 weeks, unless specifically noted. Questionnaires may be completed online through REDCap, or on paper. Paper questionnaires may be mailed with a provided self-addressed stamped envelope or brought to clinic if participant opts for clinic visits.

Protocol 10045

- **Demographics, health history, and habits** (Demographics and health history at baseline only): Information will be collected on demographics, medical history, and health habits including medication use, tobacco use, and use of complementary and alternative therapies via a questionnaire.
- **7-day Physical Activity Log:** Participants will complete a seven-day Physical Activity Log (for the preceding 7 days) at baseline (before randomization) and 24-week assessments. Physical Activity Logs of exercise during the seven days preceding the assessment point will be used to determine minutes per week of moderate physical activity.
- Assessment of physical activity prior to ovarian cancer diagnosis (baseline only): Questions 6-8 of Form 34 v2: Personal Habits Questionnaire used by the Women's Health Initiative (https://www.whi.org/researchers/studydoc_layouts/15/WopiFrame.aspx?sourcedoc=/researchers/studydoc/WHI%20Forms/F034%20v2.pdf&action=default) will be included to assess the participant's estimated level of physical activity in the 2 years prior to their diagnosis of ovarian cancer.
- **Perceived Stress Scale (82):** This instrument uses a Likert-type rating scale to measure the degree to which situations in life are perceived as stressful, specifically unpredictable, uncontrollable, and overloading. The scale has excellent psychometric properties and relates to relevant outcomes in expected ways. Internal consistency is high with Chronbach's alpha's ranging from 0.75 to 0.86.
- **Hospital Anxiety and Depression Scale, anxiety and depression (HADS-A and HADS-D) subscales (83, 84):** This instrument is a well validated and widely used assessment of anxiety and depression. The 14-item scale has two subscales, anxiety and depression, derived from 7 questions each. Participant responses are scored on a scale of 0 to 3 with variable anchors (85). The Internal reliability is high with Chronbach's alpha for the anxiety scale ranging from 0.89-0.93 and 0.86-0.90 for the depression scale (83, 84).
- **The Cancer Worry Scale** is a widely used, four-item scale that assesses the extent to which worry about cancer interferes with daily functioning (86). The items have been adapted to measure worry about cancer recurrence specifically (87). Response options range from 1 ("rarely or not at all") to 4 ("a lot"). The sum of the responses is computed to create a cancer worry score. In a large, community based sample of over 1300 women, the Chronbach's alpha for this scale was 0.73.
- **Health-related Quality of Life:** Health related quality of life will be measured using the RAND 36-Item Short Form Health Survey from the Medical Outcomes Study (88, 89). This survey is a well-validated instrument that assesses eight aspects of health related quality of life and has been used in previous research investigating the effect of exercise on ovarian cancer survivors (90). Specifically, physical functioning, bodily pain, role limitations due to physical health problems, role limitations due to personal or emotional problems, emotional well-being, social functioning, energy/fatigue, and general health perceptions are assessed in 36 questions. Participants respond on either a binary yes/no or Likert response scale. Chronbach's alpha is sufficient ranging from 0.78-0.93 for the 8 constructs. Ovarian cancer-specific quality of life will be assessed using the Functional Assessment of Cancer Therapy -Ovarian (FACT-O) (91). The Chronbach's alpha for this scale was 0.92.
- **Fatigue:** will be assessed using the Functional Assessment of Cancer Therapy Fatigue Scale as measures of fatigue have a well-known negative association with quality of life. This scale is a 13-item scale used to assess sleep disturbances and patterns associated with fatigue specifically in cancer patients and survivors (92, 93). Participants respond on a 5-point Likert scale from 0 (not at all) to 5 (very much). It has previously been used to detect significant differences in fatigue among ovarian cancer survivors (94-96). It has acceptable reliability with a Chronbach's alpha of 0.93 and a test-retest correlation of 0.87.
- **Sleep:** The Pittsburgh Sleep Quality Index is a 19-item measure providing a comprehensive picture of sleep quality. Specifically, 7 components representing subjective sleep quality, sleep latency, sleep duration, sleep efficiency, sleep disturbance, use of sleep medication, daytime dysfunction are derived from the scale in addition to an overall global sleep quality score (97, 98). Participant responses range from 0 (no difficulty) to 3 (severe difficulty). Reliability of the scale ranges from 0.77-0.81 and construct validity is sufficiently discriminating (97, 99).
- **Theory of Planned Behavior Constructs:** A 7-item questionnaire developed by Azjen (2006), used to assess the role of TPB in an exercise intervention for ovarian cancer survivors (100), will be used to assess the primary constructs of the Theory of Planned Behavior (101). Each will be measured on a 7-point Likert scale and reflect the intention, attitude, subjective norm, and perceived behavioral control of physical activity. Additionally, underlying beliefs will be assessed with open-ended questions asking about perceived advantages of exercise and barriers to exercise based on Azjen (2006). These assessments will help us understand predictors of adherence to each of the exercise interventions and thus will be used to inform the design of future studies.
- **Food Frequency Questionnaire** (at baseline and 24 weeks only): Persons adopting an exercise program may change their diet, to include increased caloric intake, especially carbohydrates (102, 103). Because dietary changes could be associated with changes in biomarkers, we will obtain accurate baseline and follow-up data on dietary

Protocol 10045

intake, to document the extent and character of any dietary change. Both intervention and control participants will be carefully counseled that this is not a dietary study, and that they should not significantly change their dietary intake or composition. It will ascertain dietary habits for the preceding month.

Research specific labs

- **Blood specimens:** Blood will be collected for VEGF and IL-6, and will be assayed at the Department of Laboratory Medicine, Children's Hospital Boston, using validated commercial Enzyme Linked Immunosorbent Assays from R&D Systems.(104) We will also collect and store blood for future assays. Participants will be asked to refrain from alcohol, moderate/vigorous exercise (24 hours) or NSAID use (24 hours) prior to a fasting (no food/drink other than water for 12 hours) venous blood collection (up to 50mL), and processed within 1 hour of collection at the FHCRC Specimen Processing lab. Serum and plasma aliquots, buffy coat, packed red blood cells, peripheral blood mononuclear cells, and RNA later collection vials will be stored at -80°C. All specimens will be labeled with the participants' specimen ID number. Participants who opt against a clinic visit will be provided with blood tubes, instructions, and necessary shipping materials to be taken to a local laboratory. They will get their blood drawn at the local laboratory and the local laboratory will process the blood for serum, plasma, and when able, buffy coat per standardized instructions. Other specimens (RNA later, peripheral blood mononuclear cells) will be omitted. Processed specimens will be refrigerated until pick-up and shipped that day ([expedited overnight shipping](#)) on ice to the FHCRC Prevention Center for aliquoting and storage by the Prevention Center.
- **Salivary Cortisol:** Participants will collect saliva samples at bedtime for 3 consecutive days at home. They will be asked to refrain from food, drink, caffeine, and exercise for 30 minutes before sample collections, and will be instructed to refrain from brushing or flossing teeth prior to sample collection. They will collect the saliva samples using the "passive drool" method. Sterile cryovials are fitted with a mouthpiece (Saliva Collection Aid) provided in the collection kit (Salimetrics, Carlsbad, CA). Participants are instructed to allow saliva to pool in the mouth. With head tilted forward, participants should drool through the Saliva Collection Aid to collect saliva in the 2 mL cryovial. The procedure is repeated until sufficient sample is collected. They will record the date and time of collection on the vial. Samples will be stored at room temperature by participants, until they can bring samples to the Prevention Center Clinic for their other assessments. At the Prevention Center, they will be placed in the -80°C freezer for long-term storage until assays are ready to be performed. [Participants who opt against a clinic visit will be provided with shipping materials, and the samples will be shipped overnight to the Prevention Center and placed in the -80°C freezer for long-term storage until assays are ready to be performed.](#)
- **Urinary norepinephrine:** Participants will collect urine over 24 hours. They will store the urine in provided bottles in their refrigerator (or cooler with ice pack) until they bring the collected urine to the Prevention Center for their clinic visit. At the Prevention Center, the sample volume will be recorded. EDTA (final concentration 1 mM) and sodium metabisulfite (final concentration 4 mM) will be added to the samples in order to prevent catecholamine degradation, and samples will be stored at -80°C. Additional aliquots of untreated urine and urine with boric acid (25mL of urine mixed with 250mg boric acid) will also be stored for possible future assays. 24-hour urine collection may be more valid to assess chronic stress than first-morning void. Participants will receive electronic reminders to collect their urine and saliva samples. [Participants who opt against a clinic visit will not perform the 24 hour urine collection due to logistical difficulties associated with shipping urine and processing which is best done immediately rather than delayed.](#)

Assays

